8.1.3 Other study parameters (if applicable)

We will collect the following maternal characteristics: age, ethnic origin, highest completed level of education, parental smoking, mode of delivery, antenatal corticosteroids, chorioamnionitis, hypertension, pre-eclampsia and multiple pregnancy. We will also present the following baseline characteristics of patients: gestational age, sex, birth weight, Apgar score at 5 minutes, surfactant therapy, patent ductus arteriosus, age at randomisation, BPD severity, time on mechanical ventilation and ventilation mode, and other major neonatal morbidities. Actual treatment at time of randomisation such as the settings of ventilatory support and/or oxygen supplementation, and medications will be recorded. All variables will be

presented as summary statistics according to allocation arm.

8.2 Randomisation, blinding and treatment allocation

Eligible patients will be randomly allocated in a 1:1 ratio to the low (90%) or high (95%) SpO₂ limit. Block randomisation will be used. All patients born in the same NICU will be clustered in 1 block; participants will be allocated to one of the treatment arms within these blocks such that an equal number are assigned to each treatment. Stratification for BPD severity will be performed. Each participant will be randomly assigned to a treatment arm using a fully GCP-compliant random number generator function, which will be centrally controlled and web-based, using a dedicated, password-protected, SSL-encrypted website (ELEA).

The protocol allows for twins and triplets to be included if meeting the inclusion criteria. For logistical reasons all infants from one family will be assigned to the same treatment arm.

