4. STUDY POPULATION

4.1 Population

Children born < 32 weeks of gestational age, with moderate or severe BPD, will be included between 36 and 38 weeks of PMA. BPD will be defined as oxygen need for ≥ 28 days from birth until 36 weeks of PMA. BPD severity will be assessed at 36 weeks PMA. Children who, at that time, need $\geq 30\%$ supplemental oxygen or depend on nasal continuous positive airway pressure (nCPAP), high flow nasal cannula (HFNC) oxygen (≥ 2 L/ min) or mechanical ventilation are classified as having severe BPD. If children need $>21\%$ oxygen but $< 30\%$ an oxygen reduction test will be performed to assess BPD severity. (3) Only children with moderate BPD according to the oxygen reduction test can be included.

The protocol allows for twins and triplets to be included if meeting the inclusion criteria. For logistical reasons all infants from one family will be assigned to the same treatment arm.

Children will be assessed for eligibility by the treating physician in the NICU where the child was born, as all children born < 32 weeks of gestational age are treated in a NICU. Between 35 and 36 weeks PMA, the local investigator of the NICU will contact the treating physician of the hospital where the child is admitted (whether this is NICU or post-IC high care unit) to determine if the child is still eligible for the study (e.g. moderate or severe BPD and still in need of supplemental oxygen). If so, the treating physician will be asked to explain the study to the parents and will provide them with parent information on the study.

Feasibility of recruitment

In the Netherlands in 2015 170.510 children were born. (21) Around 1540 of them were born < 32 weeks of gestation AND were still alive after 28 days. The incidence of BPD in children born < 32 weeks in the Netherlands is not known. Recent international data from Western Europe show a mean incidence of moderate-severe BPD at 36 weeks PMA of 22% in this group. (22) This gives an estimated number of eligible children of 339 per year in the Netherlands.

We aim to include 198 neonates over a period of 2.5 years of recruitment based on an expected response rate of 30% and allowing a drop-out rate of 10%. Every NICU will aim to include 0.3-2 children per month from their centre. The heads of all NICUs expressed their (written and signed) willingness to participate in the study.

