4.4 Sample size calculation

There have been no studies addressing our research question in children from the age of 36 weeks PMA.

A simulation study with 4 scenarios was performed to calculate how many patients are needed in order to obtain a significant differences between the 2 groups after 6 months. Our outcome is weight standard deviation score at 6 months corrected age. We assumed a mixed effect model with a random intercept to account for the correlation between the patients that come from the same hospital. We assume 10 hospital-clusters (10 NICU centres with appurtenant post IC/HC departments in the surrounding regional hospitals) with each hospital-cluster having 16 (± 3) or 18 (± 3) number of patients. The mean weight at 6 months for group 0 was assumed -1.15 SD and the mean weight at 6 months for group 1 was assume -0.65 SD since a higher weight of 0.5 SDS was considered clinically relevant. The variation in weight due to differences between individuals was assumed 1.18 SD while the variation in weight due to differences between hospitals was assumed 0.1 and 0.2 SD.

	Scenario 1	Scenario 2	Scenario 3	Scenario 4
Power	0.72	0.82	0.73	0.83
Variation of weight (hospital)	0.10	0.10	0.20	0.20
Total patients	160	180	160	180

For the actual study sample size, we will use scenario 4. This scenario has the highest power and it assumes the greatest variation of weight between different hospital clusters. This leads to a sample size for our study of 180 patients. Accounting for a drop-out rate of 10%, we aim to include 198 neonates.

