10. STATISTICAL ANALYSIS

Analyses will be performed on an intention-to-treat (ITT) basis. The ITT population includes all randomised infants, regardless of protocol deviations, and includes patients with a signed informed consent for the study who have been randomised.

Descriptive statistics will be used to describe the characteristics of the study population. Means and standard deviations will be reported (normal continuous distributed data) or medians and interquartile range (skewed continuous variables). Categorical data will be presented as percentages.

In case of missing data, every attempt will be undertaken to retrieve the data by contacting NICUs and general hospitals where the child has been admitted and by contacting the child consultation clinic (with permission of the caregivers). Missing data, if >10%, will be assumed to be missing at random and multiple imputations will be used. We do expect less than 10% missing data for the primary endpoint, weight SDS.

Significance level will be 0.05.

All analyses will be completed with the statistical software package R (free download from www.rproject.org), and SPSS/PC Statistics 21.0 (SPSS Inc., Chicago, IL, USA).

Field (

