10.1 Primary study parameter(s)

The primary endpoint is weight SDS at 6 months corrected age. Comparison between the two groups for this primary endpoint will be made using a mixed effect model with a random intercept to account for the correlation between the patients that come from the same hospital cluster.

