10.2 Secondary study parameter(s)

All secondary parameters will be assessed by linear mixed effect models for continuous outcomes or logistic mixed effect models for binary outcomes. BPD severity and weight at inclusion are considered relevant variables for the outcome weight SDS at 6 months. These variables will be included in the mixed model analysis as fixed effects.

Secondary outcomes are:

- Rates of re-hospitalisations: the rates of re-hospitalisations between the 2 groups will be assessed.
- Quality of life of the caregivers (Dutch version of the CarerQOL questionnaire) (34)
Changes in the total score of the CarerQOL between baseline and 6 months and between baseline and 12 months will be assessed.

- Infant stress (Infant Behaviour Questionnaire – Revised, IBQ-R) (35): changes in the total score of the IBQ-R between baseline and 6 months and between baseline and 12 months will be assessed.
- Weight SDS, Length SDS, Head circumference SDS at 12 months corrected age, length SDS and head circumference SDS at 6 months corrected age: comparison between the two groups for these endpoints will be made.
- Length of hospital stay, length of oxygen supplementation: comparison between the two groups will be made.
- Unscheduled health care visits to the emergency department, general practitioner or paediatrician: comparison between the 2 groups will be assessed.

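### Siblings share a treatment arm, but the primary model and the power simulation allow only for hospital clustering, so the standard error is somewhat too small if sibling sets are enrolled

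*Protocol*

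**What the plan says.** Section 4.1 of the protocol states that "The protocol allows for twins and triplets to be included if meeting the inclusion criteria". Sections 4.1 and 8.2 both add that "For logistical reasons all infants from one family will be assigned to the same treatment arm". No cap on multiples and no expected share is given.

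Section 10.1 compares the arms on weight SDS at 6 months corrected age "using a mixed effect model with a random intercept to account for the correlation between the patients that come from the same hospital cluster". Section 10.2 names BPD severity and weight at inclusion as relevant to this outcome and says: "These variables will be included in the mixed model analysis as fixed effects". Section 4.4 sizes the trial on the same structure: "We assumed a mixed effect model with a random intercept to account for the correlation between the patients that come from the same hospital". The chosen scenario has 180 evaluable infants and a stated power of 0.83.

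Multiple pregnancy appears in 8.1.3 only as a maternal characteristic to be summarised by arm. The protocol nowhere mentions a family-level term, a family-clustered standard error or a design effect for siblings.

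**The concern.** Siblings share parents, gestation, feeding and home, so their weight SDS at 6 months is likely to be positively correlated beyond what a shared hospital explains. Because siblings always share an arm, that correlation does not cancel from the treatment contrast; it adds to its variance.

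The hospital intercept does not absorb it. Allocation is balanced within NICU, so hospital effects largely cancel from the contrast. On the protocol's own figures the hospital intraclass correlation is also small: 0.2² / (0.2² + 1.18²) = 0.04 / 1.43, about 0.03. The plan thus models the clustering that hardly affects the comparison and leaves out the clustering that its own allocation rule ties to treatment.

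At stake are the width of the confidence interval and the p-value for the single primary endpoint, and whether 4.4 describes the power of a valid analysis.

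**Working it through.** **Inputs from the protocol.** Difference 0.5 SDS, individual SD 1.18, hospital SD 0.2, 180 evaluable infants (4.4); 1:1 allocation (8.2); significance level 0.05 (10). Sidedness is not stated; two-sided is assumed, because one-sided testing would give power 0.88, which does not fit 0.83.

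**Inputs that are assumed.** p is the share of analysed infants whose sibling is also enrolled. rho is the sibling correlation within hospital, after covariates. The protocol gives neither, so a range is shown.

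**Step 1: the stated power.** With 90 per arm and independent infants, SE = 1.18 × √(2/90) = 0.1759, and 0.5 / 0.1759 = 2.842. Power = Φ(2.842 − 1.960) = 0.81. A simulation of the hospital random-intercept model (10 hospitals of 18, no siblings) gives 0.80. The stated 0.83 is approximately reproduced, but only with siblings treated as independent.

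**Step 2: effect of siblings.** For pairs in the same arm, the variance of the difference is multiplied by DE = 1 + p × rho.

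- Type I error of the model as written = 2 × [1 − Φ(1.96 / √DE)].
- Power of a valid family-level analysis without covariates = Φ(2.842 / √DE − 1.960).
- Rejection rate of the model as written at a true difference of 0.5 = Φ((2.842 − 1.960) / √DE).

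| p | rho | DE | Type I error, as written | Rejection rate at 0.5, as written | Power, valid family-level analysis |
|---|---|---|---|---|---|
| 7% | 0.3 | 1.021 | 5.2% | 0.81 | 0.80 |
| 10% | 0.3 | 1.03 | 5.4% | 0.81 | 0.80 |
| 20% | 0.5 | 1.10 | 6.2% | 0.80 | 0.77 |
| 30% | 0.5 | 1.15 | 6.8% | 0.79 | 0.76 |
| 40% | 0.7 | 1.28 | 8.3% | 0.78 | 0.71 |

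The true standard error exceeds the reported one by √DE − 1: about 1.5% at DE 1.03 and 13% at DE 1.28. Triplets would add more, with a factor of 1 + 2 × rho for those infants.

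**Step 3: check by simulation.** The hospital-only random-intercept model was fitted to 180 infants in 10 hospitals with siblings in one arm and no covariates (6,000 null runs per setting). Type I error was 5.1% with no siblings, 5.9% (20%, 0.5), 6.8% (30%, 0.5) and 8.4% (40%, 0.7), in line with the formula.

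**Step 4: which rows are plausible.** p is not the share of multiples; the sibling must also qualify and be enrolled. Section 4.1 quotes a 22% incidence of moderate-severe BPD in this gestational range. If 30% of enrolled infants were multiples and the chance that the sibling is also enrolled lay between 22% and 60% (both assumed), p would be 0.30 × 0.22 = 7% to 0.30 × 0.60 = 18%. With rho of 0.3 to 0.5, DE is 1.02 to 1.09 and type I error about 5.2% to 6.0%.

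**The case against.** The strongest reply concerns size. Both siblings must have moderate or severe BPD at 36 weeks, so sibling sets may be few. At an assumed 50% chance that the sibling is also enrolled, p = 40% would need 80% of enrolled infants to be multiples. Section 10.2 also adjusts for inclusion weight and BPD severity, on which siblings plausibly resemble each other, so the residual rho may be well below 0.5 to 0.7. This stands: the last row of the table is an extreme, not an expectation.

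Adjustment also reduces residual variance. An assumed correlation of 0.4 between baseline and outcome multiplies it by 1 − 0.4² = 0.84, and 0.84 × 1.18 = 0.99, so it could offset a design effect of 1.18. The simulation as described in 4.4 takes no credit for this. A reader might infer that the trial is underpowered; the documents do not establish that.

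A reader might also combine the 8.3% type I error with the power of 0.71 as one outcome. They belong to different analyses. The model as written has the inflated error and a rejection rate of about 0.78 to 0.81 at the target difference; the lower power belongs to a family-level analysis, whose type I error is not inflated.

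Finally, 10.1 is a single sentence and does not say that the hospital intercept is the only random effect, so an analysis plan not seen here could add a level. That is fair but limited: the protocol fixes both the allocation rule and a named correlation structure, the two do not match, and 4.4 has already used the hospital-only structure.

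**Conclusion.** The point holds and should be fixed. The direction is certain if at least one sibling set is enrolled and the residual sibling correlation is positive: the model as written gives an interval that is too narrow and a p-value that is too small. The size is not known from the documents. Type I error is about 5.2% to 6.2% for p of 7% to 20% and rho of 0.3 to 0.5, 6.8% at 30% and 0.5, and 8.3% only at the extreme. All of these figures assume pairs and a two-sided test.

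The power of a valid analysis is a separate matter: about 0.80 to 0.77 without covariates, and 0.71 at the extreme, against 0.81 under independence. Covariate adjustment may recover some of that loss. The documents do not support reading this as a large distortion of the primary result or as proof that 180 infants are too few.

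**What to change.** - **10.1:** add a random intercept for family nested in NICU. If it does not converge, use family-clustered robust standard errors. Name this fallback in advance.
- **10.2:** do the same for infant-level outcomes. In the logistic models, where mostly singletons and a few pairs may leave a family intercept weakly identified, use clustered standard errors. CarerQOL measures the caregiver, so siblings may carry one shared score; analyse it once per caregiver or family.
- **Data:** keep a family identifier in the analysis dataset. The allocation rule requires families to be recognised at randomisation, but the protocol does not say that the link is stored.
- **4.4:** restate the power under an assumed share of siblings and an assumed correlation, with a range, and say whether covariate adjustment is credited. No additional enrolment is proposed.

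Section 8.2 already says in substance that families are allocated together and can stay as it is. The cost is one model term and one variable, a slightly wider confidence interval and a slightly lower stated power. Making the change before the data are analysed avoids the appearance of a post hoc change to the primary model.

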8.3 Study procedures

SpO₂ profiles

As long as the child is admitted and on supplemental oxygen, SpO₂ curves will be uploaded by the local treating physician or nurse from hospital pulse oximeters and audited by the research team twice weekly. Data will be logged from the pulse oximeters by Raspberry Pi computers and stored on a USB stick, which will be secured with Bitlocker. Pseudonymised data will then be sent through encrypted file transfer to the researchers. Feedback will be given to the treating team and parents by the research team. They will be stimulated to actively wean the children from supplemental oxygen if SpO₂ is above the target for > 95% of the time. (2)

In children who will be discharged home on oxygen, the research team will obtain weekly SpO₂ curves from home pulse oximeters. If children are discharged without a pulse oximeter, which is the standard procedure in some hospitals, the research team will provide a pulse oximeter. The research team will give feedback to the caregivers directly or to the treating physician who will inform the caregivers, depending on the preference of parents and/or treating physician. Caregivers will be instructed to decrease supplemental oxygen if SpO₂ is above the target for > 95% of the time. In any case, the treating physician will be updated on changes in supplemental oxygen.

After stopping supplemental oxygen, a SpO₂ profile will be obtained after 1 week. If this profile shows SpO₂ values above the target for > 95% of the time no more SpO₂ profiles will be obtained.

If a child is readmitted to hospital while still on supplemental oxygen the lower SpO₂ limit to which the child was randomized will be kept. If children are readmitted after they stopped supplemental oxygen for at least 2 weeks, the lower SpO₂ limit will be up to the treating physician during admission.

If a child is discharged home and experiences any medical problems, the parents should contact the treating physician. Changes in oxygen supplementation will be reported to the research team.

In case of medical problems caregivers will contact their treating physician to discuss the treatment. The treating physician contacts the research team if needed (e.g. if changes in supplemental oxygen are considered).

All SpO₂ profiles are research measurements.

CarerQOL-7D

The Care-related Quality of Life instrument (CarerQol) is designed to measure and value the impact of providing informal care on carers. (34) It combines a subjective burden measure that provides a comprehensive description of the caregiving situation (CarerQol-7D) with a valuation of informal care in terms of well-being (CarerQol-VAS) (www.imta.nl). The Dutch version of the CarerQol will be used in this study, which is a 7 question and 1 page questionnaire which includes a Visual Analogue Scale. This CarerQol will be assessed during all visits and online monthly.

Weight, height, head circumference

At every visit weight, height and head circumference are measured. This is according to standard care.

IBQ-R

The Infant Behavior Questionnaire – Revised (IBQ-R), very short form, Dutch version is an instrument assessing 36 items on 3 broad scales of infant temperament. (36) The questionnaire assesses 6 domains: activity level, soothability, fear, distress to limitations, smiling and laughter and duration of orienting. The items on the IBQ-R ask parents to rate the frequency of specific temperament-related behaviors observed over the past week.

The IBQ-R is a research tool and will be assessed at all visits (0,6 and 12 months).

Multiple Breath Washout (MBW)

If available in the local NICU/ high care centre, lung clearance index (LCI) and functional residual capacity (FRC) will be measured with SF₆ as a tracer gas (Exhalyzer, Ecomedics, Switzerland) as routine clinical care at 6 months and/or 12 months corrected age. In short, the measurement will be performed in supine position. A facemask is placed over the nose and mouth of the child. SF₆, an inert gas, will be washed in until an equilibrium is established between in- and expiratory gas of a concentration of 4%. Then the washing out starts and will be finished if the concentration of SF₆ is 2.5% of the concentration after wash in. From this procedure LCI and FRC can be derived.

Chest CT scan

In addition, if available as routine care in the local NICU/ high care centre, patients will be offered a free breathing volumetric chest CT scan without sedation at 6 months corrected age according to the local routine care protocol. (31). CT scans are scored by an experienced thoracic radiologist using the quantitative Perth-Rotterdam Annotated Grid Morphometric Analysis (PRAGMA)-BPD scoring method. (37) This scoring system identifies lung tissue with a normal appearance, hypoattenuation, hyperattenuation and bronchial wall thickening and expresses their volume in ml and as percentage of total lung volume. In addition, the severity of architectural distortion of the lung, meaning an abnormal displacement of bronchi, vessels, fissures and/or septa caused by diffuse or localized lung disease, will be scored.

Cardiac Ultrasound

If available as routine care, children will be screened for pulmonary hypertension by cardiac ultrasound at 6 months corrected age. For this echocardiogram, we will use an EPIC 7C (Philips Medical Systems, Best, the Netherlands) or Vivid E9 (GE Healthcare, Wauwatosa, WI, USA) ultrasound system. Apical 4-chamber, parasternal long-axis and short-axis views will be acquired and stored. M-mode, 2D, color Doppler and pulsed wave Doppler images will be acquired to collect data on tricuspid regurgitant jet, pulmonic valve insufficiency, pulmonary acceleration time, right and left ventricular (RV and LV) dimensions and mass, shortening fraction of the LV, and fractional area change (FAC) of the RV. All measurements will be performed off-line using Xcellera (version R4.1, Philips, Best, The Netherlands).

Costs

In between visits, a monthly electronic tailor-made diary will be provided to the parents to obtain data on hospital re-admissions, oxygen supplementation, unscheduled visits to health care providers, medication, absence from work and attendance of day care between the study visits. These data will be used for the cost-effectiveness analysis.

Informed consent for follow up studies

At the last clinic visit we will ask written informed consent for follow up studies.

Table

	Visit 0 months	Visit 6 months	Visit 12 months
Weight, height, head circumference	x	x	x
CarerQOL-7D*	x	x	x
IBQ-R	x	x	x
Multiple breath washout**		x	x
Chest CT scan**		x	
Cardiac ultrasound**		x	

*also measured monthly in an online diary, together with data on admissions and absence of work

** not mandatory, if available as routine care

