5. TREATMENT OF SUBJECTS

5.1 Investigational product/treatment

We will investigate an active supplemental oxygen weaning strategy based on a lower limit of SpO₂ of 95% as compared to 90%. In the intervention group supplemental oxygen will be weaned on a lower limit of SpO₂ of 95% (lower alarm limit will be set on 94%). This limit has been chosen for several reasons. First, the median SpO₂ in well term infants and in convalescent preterm born infants is 98% and 95-97% respectively. (23) International guidelines meanwhile recommend to keep SpO₂ >93% and, setting a lower limit of 95% vs 90% will make overlap between the intervention and usual care group (the controls) as small as possible. (2, 24) As the current standard care target is 90%, in the control group, supplemental oxygen will be weaned on a lower limit of SpO₂ of 90% (lower alarm limit will be set on 89%). (25-27)

As long as the child is on supplemental oxygen, SpO₂ curves will be obtained and audited from hospital pulse oximeters by the research team twice weekly and feedback will be given to the treating team. They will be stimulated to actively wean the children from supplemental oxygen if SpO₂ is above the lower limit according to the treatment arm for > 90% of the time. In children who will be discharged home on oxygen, the research team will obtain weekly SpO₂ curves from home pulse oximeters. Feedback will be given to the caregivers in close collaboration with the treating physician and they will be instructed to decrease supplemental oxygen if SpO₂ is above the lower limit according to the treatment arm for > 90% of the time.

There is no evidence on a cut-off point for the amount of time that is accepted for an infant to saturate above or below an established limit. The British Thoracic Society Guideline for home oxygen in children suggests that the lower limit target SpO₂ should be met for at least 95% of a stable recording period.(2) However, this does not take into account that a 24 hour saturation profile made with pulse oximetry in an infant is prone to artefacts, since periods of feeding, activity and sleeping are all registered. Furthermore, Terrill et al. studied normative oximetry data in extreme preterm infants at term equivalent age. They found mean saturations of 96.1% (95.4–96.8%) with 7.56% (5.1–10.0%) of the measuring time spent below an oxygen saturation of 90%.(28, 29).

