For this reason, the time spent below the lower limit will be accepted to a maximum of 10%: when the oxygen saturation is below the assigned SpO₂ lower limit for ≥10% of the recorded time (equivalent to <90% of the time spent above the lower limit), the treating team is stimulated to increase supplemental oxygen. When the oxygen saturation is below the assigned lower limit for ≤10% of the time (equivalent to >90% of the time spent above the lower limit), the treating team will be advised to wean supplemental oxygen.

SpO₂ data can be logged in different ways:

1. Logged from the pulse oximeters and stored on a USB stick. All data downloaded from a pulse oximeter is anonymous, since no patient characteristics are saved on it. The USB stick will not be secured with BitLocker, since a pulse oximeter does not recognize BitLocker and will not log it's data on the USB device. Since only anonymous data are logged, this will not be a problem. Downloaded data will be pseudonymised with a study and patient specific number by the local researcher who logged the data. Pseudonymised data will then be sent through encrypted file transfer to the researchers.
2. In some hospitals, all clinical data derived from monitoring a patient (for instance oxygen saturation and heart rate), is automatically saved in a central server based storage and can be accessed and downloaded with permission of the hospital or department by the local researcher. If this is the case, the necessary data can be downloaded from the hospital server, instead of logging it onto a USB device. This data will also be pseudonymised and be sent to the researchers in the same way as when the data was downloaded from the pulse oximeter.

A standard operating procedure will give recommendations on weaning supplemental oxygen; this SOP will follow daily practice as closely as possible. In children on low flow oxygen, most children will have 100% oxygen and lowering flows of oxygen is the only way to wean, at least in the home situation. In this group of patients, we will recommend to start weaning by lowering flows of oxygen with 0.1 L/min/period. Once the oxygen requirement reaches 0.1 L/min, discontinuation should be considered. One week after stopping supplemental oxygen a control SpO₂ profile will be obtained and audited. If this profile shows SpO₂ > target for > 90% of the time no more SpO₂ profiles will be obtained.

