5.3 Escape medication

Deviation of the protocol is possible if according to the treating physician this is deemed necessary for urgent medical reasons. Deviations of the protocol will be discouraged if SpO₂ profiles show that SpO₂ is above the target SpO₂ for > 95% of the time. Protocol deviations should be reported to the research team with the reasons for deviation from the

protocol. Deviation from the protocol because of failure to thrive is not allowed, as growth is our primary endpoint. Analysis will be on an intention-to-treat basis.

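### Sections 5.1 and 8.3 of the protocol set different thresholds (>90% and >95% of time above the limit) for the same three oxygen decisions, and nothing says which prevails

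*Protocol*

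**What the plan says.** **Section 5.1.** Staff in hospital are encouraged to wean, and caregivers at home are told to reduce oxygen, "if SpO₂ is above the lower limit according to the treatment arm for > 90% of the time". The section then discusses a guideline figure of at least 95% of a stable recording, explains why it accepts more time below the limit than that, and restates its own rule: "equivalent to >90% of the time spent above the lower limit), the treating team will be advised to wean supplemental oxygen". The trigger for raising oxygen is "when the oxygen saturation is below the assigned SpO₂ lower limit for ≥10% of the recorded time". For the check one week after oxygen is stopped: "If this profile shows SpO₂ > target for > 90% of the time no more SpO₂ profiles will be obtained".

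**Section 8.3.** Feedback to the treating team is to encourage them to "actively wean the children from supplemental oxygen if SpO₂ is above the target for > 95% of the time", with a citation to the same guideline that 5.1 discusses. The instruction to caregivers at home and the rule for ending profiles after oxygen is stopped also use >95%. Section 8.3 has no rule for increasing oxygen.

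**Section 5.3.** "Deviations of the protocol will be discouraged if SpO₂ profiles show that SpO₂ is above the target SpO₂ for > 95% of the time". This is about physician deviations, not about when to wean.

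**The concern.** The randomised contrast is the lower SpO₂ limit, 95% against 90%. The time-above-limit criterion turns that limit into advice to reduce oxygen in both arms. If two sections of the protocol state that criterion differently, the strategy under test is not uniquely defined.

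Four things depend on which section is followed:

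- **Oxygen exposure and duration.** Length of oxygen supplementation is a secondary outcome (8.1.2).
- **The advice given.** Under 8.4, failure to follow the research team's advice at least three consecutive times leads to withdrawal. Under 8.5, infants withdrawn before oxygen is stopped are replaced. The link is indirect, because 8.4 refers to advice actually given, but the threshold decides what that advice is.
- **When monitoring by profile ends** after oxygen is stopped.
- **Reproducibility.** A reader of the eventual report could not tell from this protocol which weaning strategy was tested.

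**Working it through.** The plan gives no calculated figure to reproduce here, so the check sets the rules side by side.

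**Inputs.** Let A be the percentage of recorded time above the assigned limit and B = 100 − A the percentage below it. The protocol uses lower limit and target interchangeably: its objectives describe targeting in terms of the lower limit, and 5.1 itself uses target for the post-cessation check. The two terms are therefore read as the same quantity.

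**Step 1: the same three decisions.**

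| Decision | 5.1 | 8.3 |
|---|---|---|
| Wean in hospital | A > 90 | A > 95 |
| Wean at home | A > 90 | A > 95 |
| End profiles after oxygen is stopped | A > 90 | A > 95 |
| Increase oxygen | B ≥ 10 (A < 90 in parentheses) | no rule |

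**Step 2: where they differ.**

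| A | 5.1 | 8.3 |
|---|---|---|
| below 90 | increase | no trigger to wean |
| above 90, up to and including 95 | wean; end profiles | no trigger to wean; condition for ending profiles not met |
| above 95 | wean; end profiles | wean; end profiles |

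The sections disagree for every profile with 90 < A ≤ 95, in both arms. If a recording holds a full 24 hours of valid signal (an assumption; 5.1 mentions 24-hour profiles), 5% is 0.05 × 24 = 1.2 hours and 10% is 0.10 × 24 = 2.4 hours. The disputed band is then at least 1.2 but less than 2.4 hours below the limit.

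**Step 3: direction.** A > 95 implies A > 90, but not the reverse. At any one audit, every profile that qualifies for weaning under 8.3 also qualifies under 5.1, and some qualify only under 5.1. For the same profiles, advice to wean can come no later under 5.1 than under 8.3. The documents do not allow the difference in days of oxygen to be computed.

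**Step 4: can both rules stand together?** One could try three zones: wean above 95%, hold between 90% and 95%, increase below 90%. Section 5.1 rules this out, because it advises weaning as soon as A exceeds 90.

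**Step 5: are such profiles plausible?** Section 5.1 cites 7.56% (5.1–10.0%) of time below 90% in extreme preterm infants at term-equivalent age. In terms of A this is 100 − 7.56 = 92.44%, with ends 100 − 10.0 = 90.0% and 100 − 5.1 = 94.9%. The central value lies inside the disputed band.

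**Step 6: boundary within 5.1.** At B = 10 exactly, the text triggers an increase (≥10% below) and also weaning (≤10% below). The equivalents in parentheses (<90% and >90% above) cover neither case at A = 90. The overlap is a single point.

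**The case against.** Several stronger readings are tempting, and the protocol does not support them.

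- **Opposite advice.** A reader might infer that one profile gets contrary instructions. Section 8.3 has no rule for increasing oxygen, so between the two sections the conflict is wean against no trigger to wean. The only clash between increase and wean is the single point within 5.1.
- **Section 5.3 as a further statement of the weaning rule.** It covers a different decision, and a different threshold there is not in itself a contradiction.
- **The normative figure sizes the problem.** It does not. The protocol does not say whether 5.1–10.0% is a range, an interquartile range or a confidence interval. The infants are not described as having moderate or severe BPD with oxygen adjusted to a limit. The figure concerns 90% only, so it says nothing about the 95% arm.
- **Sites follow 8.3.** The text does not say so. The research team audits the curves and feeds back, and 5.1 refers to an SOP for weaning that is not shown. Central audit makes mixing between sites less likely, but it does not settle which threshold the auditors apply or whether it changed over time.
- **One arm is favoured.** Under either section the threshold is the same in both arms, and the randomised limits and alarm settings are stated consistently. An effect on the separation between arms is possible but not shown.

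It may also be said that 5.1 is evidently the later text: it argues for its own figure, and the two sections also disagree on whether the USB stick is secured with BitLocker. This suggests incomplete updating, but it is an inference. The protocol gives no rule of precedence.

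What stands after all this is the textual contradiction on three decisions.

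**Conclusion.** The point holds as an internal inconsistency that is wrong as written. Sections 5.1 and 8.3 give different thresholds for in-hospital weaning, home weaning and ending profiles after oxygen is stopped. They conflict for every profile with more than 90% and up to 95% of time above the limit, in either arm.

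The width of the band is certain; the share of trial profiles that fall in it is unknown. Nothing in the protocol shows that both thresholds have been used in practice, or that the discrepancy biases the comparison. The conclusion assumes only that target and lower limit mean the same thing. It must be fixed because the rule governs oxygen exposure in both arms and feeds a secondary outcome. Which threshold is clinically right is not judged here.

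The overlap at exactly 10% in 5.1 and the >95% in 5.3 are minor and can be dealt with in the same edit.

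**What to change.** Reconcile 5.1 and 8.3 to one stated criterion for each decision (weaning in hospital, weaning at home, increasing oxygen, ending profiles), with boundaries that neither overlap nor leave a gap. The clinical leads must choose the values. Check 5.3 and the weaning SOP against the result, and use one term for limit and target throughout.

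Establish which threshold the research team has applied in its feedback. If both turn out to have been used, record which was in force for each piece of advice and report adherence against that version.

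The cost is a wording amendment, alignment of the SOP and a short notice to sites. No extra patients or measurements are needed. The look back at past advice is needed only if recruitment has begun.
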